9.3.2. Secondary Endpoint Analyses

If the result of the primary endpoint is statistically significant, the secondary endpoints will be analyzed. The methods and procedures necessary to maintain a study-wide 2-sided type I error rate of 0.05 across primary and secondary endpoint testing will be described in the statistical analysis plan.

- Castration rate defined as the cumulative probability of testosterone suppression to ≤ 50 ng/dL (1.7 nmol/L) prior to dosing at Week 1 Day 4, and prior to dosing at Week 3 Day 1 will be summarized by treatment group using the Kaplan-Meier method;
- Profound castration rate defined as the cumulative probability of testosterone suppression of ≤ 20 ng/dL (0.7 nmol/L) while on treatment from Week 25 Day 1 through Week 49 Day 1 will be estimated for each treatment group using the Kaplan-Meier method. The difference in the cumulative probabilities between the relugolix group and the leuprolide acetate group will be provided, along with the 95% confidence interval calculated in the same manner as in the primary analysis of the primary endpoint;
- PSA response and percent change from baseline in PSA at Week 3 and Week 5 will be summarized and compared between the relugolix group and the leuprolide acetate group;
- Proportions of patients who have a PSA concentration < 0.2 ng/mL (0.2 μ g/L) at Week 25 will be summarized by treatment group. The proportions will be compared between the relugolix group and the leuprolide acetate group by constructing a 95% confidence interval for the difference in proportions;
- Time to testosterone recovery in approximately 100 patients randomized to relugolix and approximately 50 patients randomized to leuprolide acetate who complete 48 weeks of treatment and who do not start alternative androgen deprivation therapy within the following 12 weeks (or within 24 weeks following the last received leuprolide acetate 3-M depot injection) will be compared between the relugolix group and the leuprolide acetate group;
- Absolute values and changes from baseline in the scores of the EORTC-QLQ-C30 global health domain and the EORTC-QLQ-PR25 sexual activity and hormonal-treatment-related symptom subdomains will be summarized by treatment group. The least square means at Week 49 will be compared between the relugolix group and the leuprolide acetate group by constructing a 95% confidence interval for the difference in the least square means using a mixed model for repeated measures;
- Absolute values and changes from baseline of the remaining domains in the EORTC QLQ-C30 and EORTC QLQ-PR25, as well as EQ-5D-5L will be summarized by treatment group. The least square means at Week 49 will be compared between the relugolix group and the leuprolide acetate group by constructing a 95% confidence interval for the difference in the least square means using a mixed model for repeated measures;
- Time to PSA progression;
 - PSA progression is defined per Prostate Cancer Clinical Trials Working Group 3 guidelines [Scher, 2016] as the first increase in PSA of 25% or greater and 2 ng/mL or greater above the nadir with confirmation by a second PSA measurement at least 3 weeks later. For patients without declining PSA from baseline, PSA increase of 25% or greater and 2 ng/mL from baseline beyond 12 weeks will be considered PSA progression

- TCR in the subgroup of metastatic patients and the extended ITT population will only be evaluated at the time of final analysis, when approximately 390 metastatic patients have been randomized to the study and have had the opportunity to be evaluated for 48 weeks of study treatment and complete the 30-day safety follow-up visit or discontinued early. TCR will be evaluated first in the subgroup of metastatic patients at a two-sided significance level of 0.05. TCR in the extended ITT population will be tested only if the two-sided p-value in the subset of metastatic patients is < 0.05.
 - TCR is defined as the time from the date of first dose to the date of PSA progression while castrated or death due to any reason, whichever occurs earlier. TCR will be analyzed using the Kaplan-Meier method. Treatment comparison with hazard ratios will be performed using Cox proportional hazards model.

Additional details of the secondary analyses will be described in the statistical analysis plan.

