4.3.1. Inclusion Criteria

A patient will be eligible for inclusion in this study only if all of the following inclusion criteria are met prior to randomization, unless otherwise specified:

1. Has voluntarily signed and dated the informed consent form prior to initiation of any screening or study-specific procedures;
2. Is a male aged 18 years or older on the day of signing and dating the informed consent form;
3. Has histologically or cytologically confirmed diagnosis of adenocarcinoma of the prostate;
4. Is a candidate for, in the opinion of the investigator, at least 1 year of continuous androgen deprivation therapy for the management of androgen-sensitive advanced prostate cancer with one of the following clinical disease state presentations:
 - a. Evidence of biochemical (PSA) or clinical relapse following local primary intervention with curative intent, such as surgery, radiation therapy, cryotherapy, or high-frequency ultrasound and not a candidate for salvage treatment by surgery; or
 - b. Newly diagnosed androgen-sensitive metastatic disease; or
 - c. Advanced localized disease unlikely to be cured by local primary intervention with either surgery or radiation with curative intent;

Note: radiotherapy, cryotherapy, or high frequency ultrasound are allowed after 2 months of androgen deprivation therapy. Prior palliative radiation to sites other than the prostate bed is permitted.

Note: Once 915 patients are enrolled worldwide, only patients with metastatic advanced prostate cancer will be eligible for the study in all regions, except China, where both metastatic and non-metastatic patients will continue to be enrolled.

5. Has a serum testosterone at the Screening visit of ≥ 150 ng/dL (1.50 ng/mL or 5.2 nmol/L);
6. Has a serum PSA concentration at the Screening visit of > 2.0 ng/mL (2.0 μ g/L), or, when applicable, post radical prostatectomy of > 0.2 ng/mL (0.2 μ g/L) or post radiotherapy, cryotherapy, or high frequency ultrasound > 2.0 ng/mL (2.0 μ g/L) above the post interventional nadir;

Note: If patient has had a radical prostatectomy then PSA must be > 0.2 ng/mL (0.2 μ g/L) irrespective of any other treatment the patient has had.

7. Has an Eastern Cooperative Oncology Group (ECOG) performance status of 0 or 1 at initial screening and at baseline (refer to [Appendix 1](#));
8. Is a male patient who, even if surgically sterilized (ie, status post vasectomy):

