9. STATISTICAL CONSIDERATIONS AND DATA ANALYSES

A statistical analysis plan will describe the detailed statistical methods and analyses for this study. The statistical analysis plan will be prepared and finalized before database lock for the primary analysis.

There will be two analyses for the study, a primary analysis and a final analysis. The primary analysis of efficacy and safety will occur after approximately the first 915 patients have been randomized to the study and have had the opportunity to be evaluated for 48 weeks and complete the 30-day safety follow-up visit or discontinued early.

The secondary analysis will occur after approximately 390 metastatic patients have been to the study and have had the opportunity to be evaluated for 48 weeks of study treatment and complete the 30-day safety follow-up visit.

TCR in the subgroup of metastatic patients and the extended ITT population will be analyzed only at the time of the final analysis.

All confidence intervals will be 2-sided at an alpha level of 0.05 unless otherwise specified. The methodology to be used to maintain a study-wide type I error rate of 0.05 across primary and secondary endpoint testing will be described in the statistical analysis plan.

All efficacy and safety measures over the course of the study will be presented. Continuous data will be summarized by means, standard deviations, medians, maximum, minimum, and number of patients. Categorical data will be summarized by counts and percentages.

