9.1. Randomization Methods

Central randomization will be used and treatment allocation will be 2:1, relugolix to leuprolide acetate 3-M depot. Randomization will be stratified by the following factors:

- Geographic Region: North and South America versus Europe versus Asia and Rest of World;
- Presence of Metastatic Disease (metastases in regional lymph node[s] are considered N1 and will, therefore, be stratified as non-metastatic): yes versus no;
- Baseline Age: ≤ 75 years old versus > 75 years old.

Stratified efficacy analyses will incorporate these 3 stratification factors unless otherwise specified.

After the first 915 patients are enrolled, enrollment in China will continue for metastatic and non-metastatic patients until the target number of Chinese patients is reached (138 patients). In the rest of the world, only metastatic patients will continue to be enrolled until approximately 390 metastatic patients are accrued.

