9.9. Sample Size

To calculate the sample size required for the primary efficacy endpoint of this study, the following assumptions have been made:

- True probabilities of sustained testosterone suppression are 94% and 96% for relugolix and leuprolide acetate, respectively;
- 2:1 randomization ratio (relugolix:leuprolide acetate); and
- Dropout rate of 15%.

The assumed probability of sustained testosterone suppression for relugolix arm is 94%. It was estimated based on the predicted dose-response relationship for the effect of relugolix on testosterone suppression in patients with prostate cancer (data from phase 2 studies C27002 and C27003). The assumed castration rate of 96% for leuprolide acetate was based on the results from degarelix phase 3 registration program [Shore, 2013].

For Evaluation Criterion 1, 610 patients in the relugolix group will provide approximately 90% power to rule out a fixed probability of sustained testosterone suppression of < 90% at a two-sided type I error rate of 0.05.

For Evaluation Criterion 2, with the non-inferiority margin of -10% and an overall 2-sided type I error rate of 0.05, a total of approximately 915 patients (610 relugolix, 305 leuprolide acetate) will yield at least 99% power in declaring the non-inferiority of relugolix compared to leuprolide acetate.

The primary analysis will be performed separately for individual evaluation criterion using data collected through 48 weeks after enrollment of approximately 915 patients.

Approximately 915 patients will be randomized in order to fulfill the regulatory requirements of all participating countries included in the primary efficacy endpoint of this study.

The study is also powered for the secondary endpoint of TCR in the high-risk subgroup of metastatic patients. Approximately 107 confirmed castration-resistance events (PSA progressions while castrated or deaths due to any cause) will need to be observed (or approximately 390 metastatic patients will need to be enrolled) to detect a hazard ratio of 0.55 (relugolix versus leuprolide acetate) with 85% power with a two-sided type I error of 5%, assuming a castration-resistant event-free rate of 60% at 48 weeks for the control arm, an 18-month enrollment period, 12 months of additional follow-up, and a 15% dropout rate.

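### The comparison of PSA below 0.2 ng/mL names no adjustment for baseline PSA: the analysis is valid, but a more precise one is available at almost no cost

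*Protocol*

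**What the plan says.** Protocol Section 9.3.2 summarises by arm the proportion of men with PSA below 0.2 ng/mL at Week 25 and compares the arms "by constructing a 95% confidence interval for the difference in proportions". No covariate or model is named for this endpoint. The same section does name a model elsewhere: a mixed model for repeated measures for quality of life and a Cox model for time to castration resistance.

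Three general statements bear on it:

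- Section 9: "All confidence intervals will be 2-sided at an alpha level of 0.05 unless otherwise specified".
- Section 9.1: "Stratified efficacy analyses will incorporate these 3 stratification factors unless otherwise specified". The factors are region, metastatic disease and age. Baseline PSA is not one of them.
- Section 9.3.2, closing sentence: "Additional details of the secondary analyses will be described in the statistical analysis plan".

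On the starting values, inclusion criterion 6 (Section 4.3.1) reads "Has a serum PSA concentration at the Screening visit of > 2.0 ng/mL", but sets the limit for men after surgery at "post radical prostatectomy of > 0.2 ng/mL". After radiotherapy, cryotherapy or ultrasound, the requirement is more than 2.0 ng/mL above the nadir. There is no upper limit. The Schedule of Activities (Table 1-1) has PSA drawn at Screening and at Baseline Day 1.

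The timing of the endpoint is not consistent. In the protocol text that plans about 1100 patients, the objectives table in Section 3 and Section 9.3.2 give Week 25. The synopsis gives Weeks 3 and 5, both in its endpoint list and in its Statistical Methods.

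**The concern.** The endpoint is an absolute threshold, and the eligibility rules let men start at very different distances from it. A man admitted after prostatectomy may start just above 0.2 ng/mL and meet the endpoint with a small fall. A man with a high PSA needs a near-complete fall. A covariate that sets the distance to be covered is very likely to predict who arrives.

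The variable is measured in everyone before treatment, yet neither the randomisation nor the named analysis uses it. What is at stake is precision: part of the width of the reported interval comes from variation that a baseline value could explain. Chance imbalance in baseline PSA would also leave a single realised estimate harder to interpret, although it does not bias the method.

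**Working it through.** **Inputs from the protocol.** 610 and 305 patients, 2:1 allocation, 15% dropout, two-sided 0.05 (Sections 9 and 9.9).

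**Inputs not in the protocol, assumed.** The rate of PSA below 0.2 ng/mL (20% to 70%), the share of outcome variance explained by baseline PSA (R² 0.05 to 0.40), and the PSA distributions given below.

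**1. The plan's own figure.** No power or precision is stated for this endpoint. The arm sizes come from Evaluation Criterion 1, stated at about 90% power. With 610 × 0.85 ≈ 518 evaluable:

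- Φ{[(0.94 − 0.90) − 1.96·√(0.90·0.10/518)] / √(0.94·0.06/518)} = Φ{(0.0400 − 0.0258)/0.0104} ≈ 91.3%.
- The log-log and exact versions give 91.2%.

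The stated figure is reproduced. The matching leuprolide number is 305 × 0.85 ≈ 259.

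**2. Distance to the threshold.** Required fall = 1 − 0.2/baseline.

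| Baseline PSA (ng/mL) | Required fall |
|---|---|
| 0.5 | 60% |
| 2.0 | 90% |
| 100 | 99.8% |

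**3. Unadjusted half-width.** 1.96·√[p(1−p)(1/n₁ + 1/n₀)].

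- At p = 0.50 and 610/305: 1.96·√[0.25·(1/610 + 1/305)] = 6.87 points.
- Over rates of 20% to 70% it is 5.5 to 6.9 points at 610/305, and 6.0 to 7.5 at 518/259.

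**4. Approximate half-width after adjustment.** Unadjusted × √(1 − R²). At p = 0.50 and 610/305:

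| R² | Half-width (points) |
|---|---|
| 0.05 | 6.70 |
| 0.10 | 6.52 |
| 0.20 | 6.15 |
| 0.30 | 5.75 |
| 0.40 | 5.32 |

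Across all assumed rates and both sample sizes, the narrowing is about 0.1 to 1.7 points.

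**5. Simulation checks.** All use a logistic model with log baseline PSA, standardised to the marginal risk difference.

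- *Logistic outcome model, 610/305.* Control rate 30% or 50%, true difference 10 points, 800 trials per scenario. The ratio of adjusted to unadjusted standard error ran from 0.97 (R² about 0.05) to 0.79 (R² about 0.39). That is 1 − 0.97² ≈ 6% to 1 − 0.79² ≈ 38% less variance.
- *Log PSA model, 518/259, against a crude difference.* SD of log baseline PSA 1.2 to 2.0, correlation with log Week 25 PSA 0.23 to 0.80, about 52% reaching the cut-off, 18 scenarios of 500 trials. Variance fell by 3% to 46%, median about 16%.
- *Log PSA model, 518/259, against a difference stratified by metastatic status.* One third metastatic, log-PSA gap 1 to 2 between strata, 16 scenarios of 400 trials. Adding log baseline PSA cut variance by 2% to 38%, median 9% to 10%. A separate simulation of the same comparison gave 1% to 33%, median about 10%.

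Mean estimates with and without adjustment agreed within about 0.002 in the log PSA simulations.

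**6. Validity of the stated analysis.** In the logistic simulations the unadjusted difference averaged 0.098 to 0.101 against a true 0.10, and its 95% interval covered 93% to 96%.

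**The case against.** The strongest reply is that Section 9.3.2 leaves further detail to the statistical analysis plan, where the covariates of a secondary binary endpoint are commonly fixed. The quoted sentence does not call the difference unadjusted, and a standardised logistic estimate also yields an interval for a difference in proportions. All of this stands. A reader might infer that the protocol rules out adjustment or stratification; it does not. The point is therefore an improvement to a method the protocol names, not an omission.

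Second, Section 9.1 may bring in metastatic status, which probably carries some of the baseline PSA information. It does not say whether this comparison is stratified. The objection is right that a gain measured against a crude difference may overstate the benefit. Against a stratified difference the median gain drops from about 16% to about 10%, and at the low end it is negligible. It does not generally vanish.

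Third, the protocol gives no PSA distribution, no expected rate and no correlation. A reader might infer from the eligibility range that baseline PSA largely decides the outcome. The range makes it very likely prognostic, but no figure in the document shows how strongly.

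**Conclusion.** The point holds as a modest efficiency gain. The named comparison is a valid, conventional one, and adjusting for log baseline PSA would make it more precise while estimating the same quantity.

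The variance reduction is about 1% to 46% across all assumed settings, with a median of roughly 10% when metastatic status is already used in randomisation or analysis. A 10% cut is worth about 1/0.90 − 1 ≈ 11% more patients. These sizes depend wholly on assumed PSA distributions, and the simulated rates and correlations were set for Week 25. They would not carry over unchanged if Weeks 3 and 5 were retained.

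A reader might go further and infer that the unadjusted difference is biased, that its interval fails to cover, or that the trial is underpowered. The documents do not support this. Randomisation protects the estimate, simulated coverage was near nominal, and the protocol states no power, margin or success threshold for this endpoint.

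**What to change.** In Section 9.3.2, state that the marginal difference in the proportions with PSA below 0.2 ng/mL is estimated from a logistic model with treatment, log baseline PSA and the randomisation factors, standardised over the analysis population, with a robust or bootstrap 95% confidence interval. Keep the unadjusted proportions by arm as the descriptive summary.

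Before that, reconcile the visit. Section 3 and Section 9.3.2 say Week 25, while the synopsis says Weeks 3 and 5. Apply the adjusted analysis at whichever timing is retained.

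The cost is one sentence in the protocol, the matching text in the statistical analysis plan, and a little programming, all before database lock for the primary analysis. No new data are needed and the target of estimation does not change. If the analysis plan already adjusts for baseline PSA, aligning Section 9.3.2 with it is enough.

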
There are 2 separate evaluation criteria for the primary efficacy endpoint to support different regulatory requirements for assessing benefit:

- Evaluation Criterion 1: to determine whether the sustained castration rate for relugolix is greater than or equal to 90%. The lower bound of the 95% confidence interval for the cumulative probability of sustained testosterone suppression to castrate levels in the relugolix treatment group will be calculated and must be greater than or equal to 90% to meet this criterion.
- Evaluation Criterion 2: to establish the non-inferiority of relugolix compared to leuprolide acetate 3-M depot as assessed by the cumulative probability of sustained testosterone suppression to castrate levels. The lower bound of the 95% confidence interval for the difference in the cumulative probability of sustained testosterone suppression to castrate levels between the 2 treatment groups will be calculated and must be greater than or equal to the non-inferiority margin of -10% to meet this criterion.

The 2-sided type I error rate will be 0.05 for each individual evaluation criterion.

Secondary Efficacy Endpoints:

1. Castration rate: the cumulative probability of testosterone suppression to ≤ 50 ng/dL (1.7 nmol/L) prior to dosing on Week 1 Day 4, and prior to dosing on Week 3 Day 1;
2. Profound castration rate: the cumulative probability of testosterone suppression to ≤ 20 ng/dL (0.7 nmol/L) from Week 25 through Week 49;
3. PSA response rate: proportion of patients with a $\geq 50\%$ decrease in PSA from baseline at Week 3 and confirmed at Week 5;
4. Undetectable PSA rate: proportion of patients with PSA concentration < 0.2 ng/mL (0.2 μ g/L) at the Week 3 and Week 5 visits;
5. Time to testosterone recovery in approximately 100 relugolix-treated and approximately 50 leuprolide acetate-treated patients who complete 48 weeks of treatment and do not start alternative androgen deprivation therapy within 12 weeks after the last dose of relugolix or within 24 weeks following the last received injection of leuprolide acetate. Kaplan-Meier methods will be used to describe survival distributions;

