- Patients who have started alternative androgen deprivation therapy will not participate in the 60- and 90-day Follow-up visits. For approximately 100 patients receiving relugolix and approximately 50 patients receiving leuprolide acetate who complete 48 weeks of study drug treatment and, in the opinion of the investigator, can remain off androgen deprivation therapy for 90 days will be included in the testosterone recovery 60- and 90-day Follow-up visits.
- For patients assigned to the relugolix treatment arm, the patient should be called 7 days before their next visit to check on compliance with their study medication. Study drug accountability will be conducted at visits and results will be recorded as the primary source of study drug accountability.
- If patient terminates early from study treatment, the patient should be asked to come in as soon as possible and complete this visit.
- The informed consent form must be signed before any study-mandated procedures are performed.
- 12-lead ECGs should be read locally by a qualified physician.
- A complete physical examination should be performed. Visual acuity will be evaluated by a standard visual eye chart. The patient should wear any prescribed glasses or contacts during the visual acuity assessment. Patients whose presenting visual acuity score is 90 or lower at the screening visit should be encouraged to obtain a diagnostic evaluation from an eye care provider (ie, an ophthalmologist or an optometrist). Any findings (ie, diagnoses) from the eye examination should be recorded as medical history. Patients whose presenting visual acuity score at Week 25, Week 49, or Early Termination has decreased by 10 or more points from the screening visit should be referred to an ophthalmologist for a diagnostic evaluation. A copy of the ophthalmology consultation must be submitted to the sponsor.

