
 To evaluate the time course and change in serum testosterone during treatment with relugolix; 	
 Describe effects on serum testosterone: 
 Castration rate defined as the cumulative probability of testosterone suppression to ≤ 50 ng/dL (1.7 nmol/L) prior to dosing on Week 1 Day 4 and prior to dosing on Week 3 Day 1; Profound castration rate defined as the cumulative probability of testosterone suppression to ≤ 20 ng/dL (0.7 nmol/L) while on treatment from Week 25 Day 1 through Week 49 Day 1);

Objectives	Endpoints

 To evaluate the time course and magnitude of PSA reduction during treatment with relugolix; 	
 Describe effects on PSA: 
 Proportion of patients with confirmed PSA response (by Prostate Cancer Clinical Trials Working Group 3 [Scher, 2016]) at the Week 3 and Week 5 visits; Proportion of patients with PSA concentration < 0.2 ng/mL [0.2 µg/L] at the Week 25 visit;

 To evaluate testosterone recovery following discontinuation of relugolix; 	
 Time to testosterone recovery in approximately 100 patients randomized to relugolix and approximately 50 patients randomized to leuprolide acetate who complete 48 weeks of treatment and who do not plan to start alternative androgen deprivation therapy within the following 12 weeks (or within 24 weeks following the last injection of leuprolide acetate 3-M depot);

 To evaluate quality of life using validated patient-reported outcome instruments; 	
 Absolute values and changes from baseline in the scores of the EORTC-QLQ-C30 global health domain, and the EORTC-QLQ-PR25 sexual activity and hormonal-treatment-related symptom subdomains, at regular intervals during treatment, and as applicable during the Follow-up and/or End of Treatment visits; Absolute values and changes from baseline of the remaining domains in the EORTC QLQ-C30 and EORTC QLQ-PR25, as well as the EuroQol EQ-5D-5L questionnaire, at regular intervals during treatment, and as applicable during the Follow-up visits;

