4.7. Removal of Patients from Therapy

Patients may withdraw consent to participate in the study and discontinue treatment at any time for any reason. Investigators or the medical monitor may remove patients from therapy under this protocol for reasons of safety and/or lack of compliance as discussed below. Patients removed from therapy for any reason will undergo the assessments for the Week 49 visit on the Schedule of Activities. The End of Treatment is defined as the last dose of relugolix or 12 weeks after the last leuprolide acetate injection.

Follow-up visits to assess safety will be performed in all study patients. If the patient plans to start alternative androgen deprivation therapy less than 30 days after the End of Treatment visit, the Safety Follow-up visit may occur earlier, before the start of the alternative androgen deprivation therapy. Testosterone recovery will be evaluated in approximately 100 patients randomized to relugolix and approximately 50 patients to leuprolide acetate who complete 48 weeks of study drug treatment and, in the opinion of the investigator, are candidates for intermittent androgen deprivation therapy and will not be offered alternative androgen deprivation therapy upon completion of study therapy. These patients will return for the 60- and 90-day follow-up Testosterone Recovery visits.

The safety and/or compliance events shown in [Table 4-1](#) will result in the removal of patients from therapy either permanently or until the etiology of the problem has been identified and resolved.

Table 4-1 Removal of Patients from Treatment

Reason	Comment
Adverse event or intercurrent illness	Any intolerable adverse event to the patient that cannot be ameliorated by the use of adequate medical intervention, or that in the opinion of the investigator or medical monitor would lead to undue risk to the patient if dosing continued
Failed to meet eligibility criteria post randomization	If it is discovered after randomization that a patient failed to meet protocol entry criteria and continued participation poses an unacceptable risk to the patient's health
Dose hold	Relugolix dose hold that exceeds 10 consecutive days

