6.4. Follow-up Period

The study day in which the Follow-up visit occurs is relative to when the patient takes his last dose of study drug. The End of Treatment is defined as the last dose of relugolix or 12 weeks after the last leuprolide acetate injection.

30-Day Safety Follow-up Visit (Visit Window ± 7 Days)

A Safety Follow-up visit should occur 30 days after the End of Treatment and may occur earlier for patients who are starting alternative androgen deprivation therapy or do not complete 12 weeks of study treatment. Adverse events should continue to be collected and recorded through 30 days after the last dose of study drug or the date of initiation of another investigational agent or hormonal therapy or surgical intervention, whichever occurs first. Serious adverse events and concomitant medications will be collected from the signing of the informed consent form until the Safety Follow-up visit approximately 30 days after the last dose of study drug.

All other study procedures should be completed before the start of alternative androgen deprivation therapy.

The following assessments will be performed:

- Patient-reported questionnaires
 - Patients will complete the questionnaires on the tablet provided before other study procedures, such as blood draws and physical examinations, are performed;
- Vital signs and weight;
- 12-lead ECG;
- ECOG performance assessment;
- Symptom-based physical examination;
- Laboratory collection (see Section 1.1); and
- Concomitant medications and adverse events.

Testosterone Recovery Visit (Visit Window ± 7 Days)

Patients who have started alternative androgen deprivation therapy will not participate in the 60- and 90-day follow-up visits. Approximately 100 patients randomized to receive relugolix and approximately 50 patients randomized to receive leuprolide acetate who complete the 48 weeks of study drug treatment and, in the opinion of the investigator, are candidates for intermittent androgen deprivation therapy will be included in the Testosterone Recovery 60- and 90-day Follow-up visits. These patients will discontinue relugolix after 48 weeks of treatment and will be offered a period off androgen deprivation therapy.

The following assessments will be performed:

- Patient-reported outcome questionnaires
 - Patients will complete the questionnaires on the tablet provided before other study procedures, such as blood draws and physical examinations, are performed;
- Vital signs;

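### The testosterone-recovery set is defined both by intention at end of treatment and by a later event; the later-event version selects on what happens inside the recovery window

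*Protocol*

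**What the plan says.** The protocol describes the patients who contribute to time to testosterone recovery in three ways.

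- **Intention.** The endpoint table in Section 3 takes completers of 48 weeks "who do not plan to start alternative androgen deprivation therapy within the following 12 weeks". The synopsis list of secondary endpoints has the same wording.
- **Investigator's prospective judgement.** Section 4.7 takes completers who, "in the opinion of the investigator, are candidates for intermittent androgen deprivation therapy and will not be offered alternative androgen deprivation therapy" after study therapy. Footnote c of the Section 1.1 schedule takes those who "can remain off androgen deprivation therapy for 90 days". Section 6.4 also rests on candidacy for intermittent therapy.
- **Later event.** Section 9.3.2 takes completers "who do not start alternative androgen deprivation therapy within the following 12 weeks", with 24 weeks from the last injection for leuprolide. Item 5 of the synopsis's secondary efficacy endpoints likewise takes those who "do not start alternative androgen deprivation therapy within 12 weeks after the last dose of relugolix", again with the 24-week counterpart.

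Section 9.3.2 gives the size as "approximately 100 patients randomized to relugolix and approximately 50 patients randomized to leuprolide acetate" and says that recovery time "will be compared between the relugolix group and the leuprolide acetate group". The synopsis names Kaplan-Meier methods. Section 6.4 adds: "Patients who have started alternative androgen deprivation therapy will not participate in the 60- and 90-day follow-up visits". The file holds two versions of the protocol, and both show the same split between intention and event.

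**The concern.** The first two definitions can be applied on the day treatment ends. The third cannot: membership depends on whether a man starts other androgen deprivation during the period in which his recovery is being timed. The populations differ. A man who meant to stay off therapy, is found recovered at the 60-day visit and starts other therapy on day 70 is in the set under Section 3 and out of it under Section 9.3.2, although his event was observed.

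New androgen deprivation suppresses testosterone, so a man who starts before recovering can no longer be seen to recover. A man who has recovered may start because of it. Either link makes the later-event rule informative about the outcome, and if recovery differs between arms the exclusions can fall unequally. Kaplan-Meier estimation does not need the exclusion, since it can use each man's follow-up until he starts other therapy. At stake is a between-arm comparison on a secondary endpoint.

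**Working it through.** The protocol gives no power, effect size or restart rate for this endpoint, so there is no planned figure to reproduce.

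**1. Do the windows overlap the outcome?** Visit days come from Section 1.1, with nominal end of treatment at Day 337.

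- Leuprolide: last injection Day 253 + 24 × 7 = Day 421.
- Relugolix: Day 337 + 12 × 7 = Day 421.
- Last recovery visit: Day 337 + 90 = Day 427.

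The two arms' windows agree with each other. The condition covers 84 of 90 days (84/90 = 93%), so it selects on an event inside the outcome window.

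**2. Simple illustration for one arm.** Input from the protocol (Section 2.2.4.2): in phase 2 study C27003, about 50% of relugolix patients had recovered 12 weeks after stopping. Assumed: a fraction a of recovered men and b of unrecovered men start other therapy within the window. The recovered proportion among those kept is 0.5(1 − a) / [0.5(1 − a) + 0.5(1 − b)].

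| a | b = 0 | b = 0.05 |
|---|---|---|
| 0.1 | 47.4% | 48.6% |
| 0.2 | 44.4% | 45.7% |
| 0.3 | 41.2% | 42.4% |

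The standard error at n = 100 is √(0.25/100) = 5 points. The shifts, 1.4 to 8.8 points, are about 0.3 to 1.8 standard errors.

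**3. Simulation of both arms.** It used 1,000,000 men per arm, exponential recovery and Kaplan-Meier estimates at day 90. True 90-day recovery was 50% against 6%. The 6% is the degarelix figure from C27003 and stands in for a slow-recovering arm; it is not a leuprolide estimate. Restart rates, stated per 84 days, are assumptions.

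| Who starts other therapy | Excluded, fast / slow arm | Estimate under the later-event rule | Difference |
|---|---|---|---|
| Independent of recovery, 20% | 20.0% / 20.0% | 50.0% vs 6.0% | 44.0 points |
| Only after recovery, 50% | 14.6% / 1.6% | 41.5% vs 4.5% | 37.0 points |
| Only after recovery, 80% | 25.9% / 2.8% | 32.6% vs 3.2% | 29.3 points |
| Only before recovery, 20% | 14.9% / 19.4% | 52.9% vs 6.7% | 46.3 points |

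Differences were taken before rounding. With the set fixed at end of treatment and starters censored at the start, all four scenarios returned the true values to within 0.1 point (difference about 44 points). That is partly by construction: recovery is memoryless here, and restart does not depend on testosterone that is rising but still below the recovery threshold.

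**The case against.** A reader might infer that fast recoverers restart first, so that the later-event rule understates relugolix recovery by a known amount. The documents do not support that. They give no restart rule or rate, and nothing in them says that early recoverers restart within 12 weeks. Independent restart gives no bias, and restart among unrecovered men biases the other way. Even the understated case would shrink a relugolix advantage, not create one.

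The 41–49% range in step 2 is likewise illustration only. The 50% comes from 24 weeks of treatment around radiotherapy, against 48 weeks here. A recovery first seen at the 90-day visit can hardly prompt a restart before day 84, so applying the restart fraction to all recovered men probably overstates the effect.

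Sections 1.1, 4.7 and 6.4 pick men expected to stay off therapy, so few may start within 84 days. The set is a non-randomised group of completers under any wording. Censoring detail belongs in the SAP, to which Section 9.3.2 defers. All of this stands, and it limits the size of the problem. It does not reconcile the text: the protocol itself fixes incompatible populations, and the one attached to the comparison depends on the future.

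**Conclusion.** The contradiction is certain on the face of the current text. That the later-event version conditions on almost the whole recovery window, and discards recoveries already observed, follows from the visit days alone. Bias arises only if starting other therapy is related to recovery; this is plausible but not documented, and its direction and size are unknown. The simulated differences of 29 to 46 points around a true 44 show that the choice of set can matter under the assumed rates. They do not estimate what it does in this trial. The point concerns one secondary endpoint with no stated power. It is worth settling before recovery data are examined, because the trial is open-label and choosing between the definitions afterwards would be data-dependent.

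**What to change.** In Section 9.3.2 and synopsis item 5, use one definition fixed at end of treatment: patients who complete 48 weeks and at that point do not plan alternative androgen deprivation within 12 weeks. Bring footnote c of Section 1.1, Section 4.7 and Section 6.4 into line with it. Keep men who start other therapy later in the Kaplan-Meier analysis. Count any recovery seen before the start; otherwise censor at the last testosterone assessment before it. Because that censoring may itself be informative, add a sensitivity analysis that treats the start as a competing event.

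The cost is small but is more than rewording. Section 5.10.2 asks for alternative therapy to be recorded only if begun within 30 days of the last relugolix dose. Section 6.6.2.6 stops medication recording 30 days after the last relugolix dose, or 12 weeks plus 30 days after the last injection. Starters do not attend the 60- and 90-day visits, where medications would otherwise be captured. The fact and date of starting must therefore be recorded through day 90 for this subset. The later-event rule would need the same information. The change does not turn the subset into a randomised comparison.
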